## **BACKGROUND:**

Postoperative urinary retention (POUR) is a well-known risk of surgery, and is particularly common in urogynecologic surgery. While acute POUR has a high rate of eventual resolution after discharge home with a catheter for 5-7 days, this is uncomfortable and inconvenient for the patient, increases the likelihood of urinary tract infection, and increases healthcare costs. In patient surveys, being discharged home from the hospital with a catheter is considered to be a surgical complication, and is rated as one of the worst potential aspects of surgery. Reported rates of POUR in urogynecologic surgery are variable, ranging from 21-50% (1, 2, 3). In our practice the rate is estimated to be around 30%. Risk factors for developing POUR in this population have been identified, most notably high grade cystocele, higher intra-operative blood loss, urinary retention prior to surgery, and early removal of foley catheter in elderly patients (1, 2). The etiology for POUR is not completely understood, but multiple factors are suspected to play a role including postoperative pain resulting in impaired relaxation of pelvic floor muscles, decreased bladder detrusor muscle contraction, and involuntary contraction of the external urethral sphincter secondary to pain, trauma, or inflammation (4).

Research has not provided a means to prevent POUR in this patient population. One therapy that has been studied in other fields is use of an alpha receptor antagonist (most commonly tamsulosin), with the goal of relaxing musculature in the bladder neck and urethra. The bladder neck and female urethra are known to express alpha receptors. Inhibition of these receptors causes relaxation of muscle in the bladder neck and urethral sphincter, decreasing urethral pressure. Studies of alpha blockade have shown decreased mean and maximal urethral pressure 6 hours after administration of 0.4mg tamsulosin in women with lower urinary tract symptoms (5), and increased mean urinary flow rate and lower urinary tract symptoms after daily tamsulosin for one month (6). Metaanalysis and systematic review of over 700 women receiving tamsulosin reveals improvement in lower urinary tract symptoms in patients with dysfunctional voiding (7)

Tamsulosin has been studied in other surgical fields to decrease POUR. Medani et al studied men undergoing urologic surgery including varicocelectomy, inguinal herniorrhaphy, and scrotal surgery, and randomized patients to placebo versus tamsulosin 0.4mg at 14 and 2 hours before surgery, and 10 hours after surgery. They observed a decrease in POUR from 21.1% to 5.9% (8). A similar study of patients undergoing urologic surgery under spinal anesthesia randomized patients to tamsulosin vs alfuzosin vs placebo, and saw an improvement in the rates of POUR with both alpha antagonists compared to placebo, but no difference between the two alpha-blockers (9). A retrospective review of patients undergoing colorectal surgery revealed that patients who received perioperative tamsulosin for 3 days prior to surgery and after surgery were significantly less likely to experience urinary retention (6.7% vs 25%) (10). In a small, retrospective study of our own patients, tamsulosin use was associated with a significantly lower rate of POUR (OR 0.11, p=0.03).

Development of POUR is of significant consequence to patient health and well-being, as well as to healthcare costs. The risk of POUR in patients undergoing female pelvic reconstructive surgery is high. Risk factors for POUR in this field have been identified, but there are no available prevention strategies. Tamsulosin has been studied in other surgical fields and has been shown to be beneficial to preventing POUR. Determining if tamsulosin is beneficial in preventing POUR in female pelvic reconstructive surgery is a significant step in improving healthcare in this field.

## **PURPOSE/HYPOTHESIS**

The purpose of this study is to determine if perioperative use of tamsulosin decreases the risk of postoperative urinary retention after urogynecologic surgery.

Study aim 1: Compare the rates of passage of initial postoperative voiding trial.

Study aim 2: Compare the rates of any required bladder catheterization in the postoperative period

Study aim 3: Compare rates of UTI in the postoperative period

Hypothesis: Participants who have received perioperative Tamsulosin will have lower rates of postoperative urinary retention following urogynecologic surgery compared to patients who have received placebo.

**DESIGN:** Randomized Controlled Trial.

**SETTINGS:** Two large academic Institutions.

## **EXPERIMENTAL DESIGN AND METHODS:**

This will be a multi-institutional randomized controlled trial. Written consents explicitly explaining the risks and benefits of the study will be obtained from the patients.

The **inclusion** criteria are the following:

- Patients must be 18 years or older as well as willing and able to provide informed consent
- Patients must be undergoing a scheduled surgery for pelvic organ prolapse or urinary incontinence
- Standard postoperative plan must include admission to the hospital with foley catheterization overnight the night after surgery, and planned removal of foley catheter and active voiding trial on postoperative day 1.

The **exclusion** criteria are the following:

- Patient unable or unwilling to provide informed consent
- Severe allergy to sulfa drugs
- Known allergy to tamsulosin or another alpha antagonist medication
- History of urinary retention

- Planned bladder catheterization greater than 24 hours after surgery
- Known untreated UTI prior to surgery
- Current use of alpha antagonist medication for hypertension
- End stage renal or liver disease

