- Data collected will include: Study number, MRN, age, race, BMI, current tobacco use, parity, ASA class, preoperative history of urinary retention, preoperative prescription for medication for overactive bladder or urge incontinence, urodynamic testing results (presence of stress urinary incontinence and detrusor activity, increased EMG recruitment, post-void residual, peak flow rate, detrusor pressure at peak flow rate), preoperative diagnosis particularly of stress urinary incontinence or pelvic organ prolapse, surgery performed, surgical complications, estimated blood loss, voiding trial results, presence of POUR, time until resolution of POUR, presence of postoperative urinary tract infection, results of postoperative Voiding Symptom Survey.

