## **Data security**

-Study data will be collected and managed using REDCap electronic data capture tools. REDCap (Research Electronic Data Capture) is a secure, web-based application designed to support data capture for research studies, providing: 1) an intuitive interface for validated data entry; 2) audit trails for tracking data manipulation and export procedures; 3) automated export procedures for seamless data downloads to common statistical packages; and 4) procedures for importing data from external sources. Identifiable information will be stored in password protected directory accessible only by study personnel. Finally, no identifiable information will be shared outside of our institution and all non-identifiable information will be pooled and released as a group for the final study after statistical analysis is complete. After the completion of the statistical analysis phase and a sufficient length of time, the file containing the patients' MRNs and study specific unique numerical identifiers will be deleted. Patient MRN and unique study specific identifier will be kept until completion of data analysis or >2 years, whichever is greater. The file containing study specific identifier and other study, as well as pooled statistics data, will be kept for a period of greater than 3 years per policy to allow additional statistical analysis as may be required for final manuscript revisions. Every attempt to obtain and maintain a complete and thorough record of data points will be made by the study staff. In the event that any data is unable to be obtained from the usual protocol source, every attempt to obtain the data from additional electronic medical record sources will be made. If no data is obtainable, said data point will not be placed in statistical analysis and reported as such.

No paper records will be kept other than the consent forms which will be kept in a locked cabinet in a locked office

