## **Statistical considerations**

-Data will be evaluated with descriptive statistics, including means, medians, standard deviations, and ranges. Comparisons between the experimental and control group will be evaluated with univariate and multivariate logistic regression as appropriate. A conservative power analysis was performed and determined that a total of 118 (59 in each arm) would be required to achieve a power of 80% with an alpha error of 0.05 in order to detect a decrease in the rate of failed void trial from 30% to 10%. To account for a 15% dropout rate we will recruit 136 participants.

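### The exclusion for current alpha-antagonist use covers only use for hypertension, so a woman taking the drug class for another reason can be enrolled and assigned to placebo

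*Combined protocol and SAP*

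**What the plan says.** Two exclusion criteria under Experimental Design and Methods name the drug class. One concerns allergy. The other is the only one about use, and it is limited by indication: "Current use of alpha antagonist medication for hypertension". A separate criterion, "History of urinary retention", would remove women who take the drug because of retention.

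The Procedures section covers how study medication is supplied and taken. It does not address alpha antagonists from any other source. Its list of data to be collected includes "preoperative prescription for medication for overactive bladder or urge incontinence", but no field for alpha-antagonist use.

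The Background describes a use of tamsulosin in women that is not for hypertension: a meta-analysis found "improvement in lower urinary tract symptoms in patients with dysfunctional voiding". It also says: "In a small, retrospective study of our own patients, tamsulosin use was associated with a significantly lower rate of POUR". Statistical considerations plans 59 per arm for a fall in failed voiding trials from 30% to 10%.

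**The concern.** The trial compares tamsulosin with placebo. A placebo participant who already takes an alpha antagonist receives the drug class under test, whatever her reason for taking it. If the class works as hypothesised, her risk of failing the voiding trial is already lowered and the control rate moves toward the active rate. A user assigned to tamsulosin may gain little from the study drug. Either way the observed difference shrinks.

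At stake is some power and some attenuation of the estimated effect. Without a named field, nothing in the listed data would ensure that such women are counted or can be set aside in a sensitivity analysis.

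**Working it through.** **Inputs.** From Statistical considerations: failure rates 0.30 and 0.10, 59 per arm, alpha 0.05, power 80%. The plan does not state sidedness; two-sided is assumed because it reproduces the plan's figure. The share of users, x, and their failure risk are not in the documents. Every value of these below is an assumption.

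**The plan's own figure.** Unpooled normal approximation:

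n = (1.960 + 0.842)² × (0.30×0.70 + 0.10×0.90) / 0.20² = 58.87, so 59 per arm and 118 in total, as stated.

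Power at 59 per arm:

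- Standard error = √(0.30/59) = 0.0713, and 0.20/0.0713 = 2.805.
- Power = Φ(2.805 − 1.960) = 80.09%.
- The pooled-variance formula gives 78.25%, a gap of 1.84 points.

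**Model A: only the placebo arm shifts.** The active rate stays at 0.10. The placebo rate is 0.30 − e·x, where e is the effect in users: 0.20 (the full planned effect) or 0.10 (half).

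**Model B: users gain nothing from study drug.** They fail at rate q in both arms. The placebo rate is 0.30(1−x) + q·x and the active rate is 0.10(1−x) + q·x, so the expected difference is 0.20(1−x) for any q.

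Unpooled power (%), with the loss from 80.09% in brackets:

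| Assumed use x | 1% | 2% | 5% | 10% |
|---|---|---|---|---|
| Users among 59 women | 0.6 | 1.2 | 3 | 6 |
| A, e = 0.10 | 79.75 (0.3) | 79.40 (0.7) | 78.35 (1.7) | 76.51 (3.6) |
| A, e = 0.20 | 79.40 (0.7) | 78.70 (1.4) | 76.51 (3.6) | 72.59 (7.5) |
| B, q = 0.10 | 79.4 (0.7) | 78.7 (1.4) | 76.5 (3.6) | 72.6 (7.5) |
| B, q = 0.20 | 79.2 (0.9) | 78.4 (1.7) | 75.7 (4.4) | 70.8 (9.3) |
| B, q = 0.30 | 79.1 (1.0) | 78.06 (2.03) | 74.9 (5.2) | 69.2 (10.9) |

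Model A with e = 0.20 and Model B with q = 0.10 are the same case.

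Worked example, Model B with q = 0.30 and x = 2%:

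- Placebo 0.300, active 0.10×0.98 + 0.30×0.02 = 0.104, difference 0.196.
- Standard error = √((0.210 + 0.0932)/59) = 0.0717, and 0.196/0.0717 = 2.734.
- Power = Φ(2.734 − 1.960) = 78.06%.

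**Ranges across both models.** The loss is 0.3 to 2.0 points at 1-2% use, 1.7 to 5.2 at 5%, and 3.6 to 10.9 at 10%. For scale, under Model A the loss passes the 1.84-point gap between formulas at about 2.6% use (full effect) or 5.3% (half effect). Under Model B with q = 0.30 it has passed it by 2% use.

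**When the loss against plan is zero.** The Background says of retention: "In our practice the rate is estimated to be around 30"%. If that rate already includes such users, the planned control rate allows for them. The loss is also zero if users on placebo still fail at 30% while the active arm stays at 10%, which is e = 0 in Model A.

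**The case against.** The strongest reply is that nothing shows the gap would ever be used. The Background cites published studies of women with urinary symptoms; it does not say that women in this practice take the drug for that purpose. The retention and hypertension criteria already remove some users, and the remaining group is not sized. Randomisation balances whoever is left. The data list is not stated to be exhaustive, and where a data point cannot be obtained from its usual source, the Data security section says "every attempt to obtain the data from additional electronic medical record sources will be made".

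Most of this stands, and it limits the point to an eligibility gap of unknown and possibly negligible size. Two things remain. The retention criterion does not reach a woman who takes the drug for another reason, and balance between arms prevents confounding but not dilution. Retrieval from the record is possible, but it is not ensured for an exposure that no field asks about.

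A reader might infer from the sentence on the investigators' own patients that outside use is known to occur among women who would be eligible. That sentence does not say why or when those women took tamsulosin, how many did, or whether they had a retention history. It closes a paragraph otherwise about perioperative use to prevent retention, so use around surgery is at least as natural a reading. It is not evidence of contamination.

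**Conclusion.** As written, the criteria admit a woman who already takes the drug class under test, provided her reason is not hypertension and she has no history of retention. The expected consequence is dilution toward no difference. At 1-2% use it would cost roughly 0.3 to 2.0 points of power, and several points or more only if use reached 5-10%. These figures rest on assumed prevalences and assumed risks in users, and the loss can be zero.

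Two stronger conclusions are not supported. The primary comparison is not shown to be compromised, because contamination is possible but not demonstrated. Nor do the documents contradict themselves: a hypertension-only exclusion is compatible with a tamsulosin-versus-placebo comparison. The point is of the lowest severity, worth considering because it is cheap to close.

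**What to change.** Remove the indication limit so that the exclusion covers current alpha-antagonist use for any reason, with the investigators confirming the scope they intend. Add one named data field for any alpha-antagonist use outside study supply up to the voiding trial. If the hypertension-only wording proves to be deliberate, the field alone would let such participants be counted and examined in a sensitivity analysis.

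The cost is a minor amendment to one criterion and one extra field. The sample size stays at 118, with 136 recruited. The downside is that a few otherwise eligible patients might not be enrolled.

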## **Procedures**

- Once patients are enrolled and consents are obtained, they will be randomized into either tamsulosin or placebo group
- Investigational drug services will provide medication to the study investigators who will provide patients with their medication at the preoperative visit, which is typically 1-2 weeks prior to surgery.
- Patients will be instructed to take one pill by mouth daily for three days prior to surgery.
- While hospitalized after surgery, patients will continue to take their study medication. They will take one extra pill the morning after surgery, 3-4 hours prior to their voiding trial. Other than this one extra dose, they will continue taking one pill every evening after dinner until their medication has run out. This will total 3 days prior, and 6 days after surgery.
- The voiding trial, which is standard practice after urogynecologic surgery, will be performed the morning after surgery. This will include filling the bladder with 300cc of normal saline or sterile water retrograde through the foley catheter, then removing the catheter. The patient will have 15 minutes to void. The volume of their void will be measured. If they void 200ml or greater, they have passed the voiding trial. If they void less than 200ml or cannot void at all, they have failed the voiding trial and the catheter is reinserted with plans to remove it in the office in 4-6 days. If the void is not measured or cannot be measured for any reason, an ultrasound of the bladder will be performed to determine the post-void residual volume in the bladder with a threshold of must void 2/3 of instilled volume.
- The patient will complete the Voiding Symptom Survey at time of enrollment and again on postoperative day 4. They will be provided with a copy of this form prior to their discharge from the hospital. They will be contacted via telephone to report their results.
- Data collected will include: Study number, MRN, age, race, BMI, current tobacco use, parity, ASA class, preoperative history of urinary retention, preoperative prescription for medication for overactive bladder or urge incontinence, urodynamic testing results (presence of stress urinary incontinence and detrusor activity, increased EMG recruitment, post-void residual, peak flow rate, detrusor pressure at peak flow rate), preoperative diagnosis particularly of stress urinary incontinence or pelvic organ prolapse, surgery performed, surgical complications, estimated blood loss, voiding trial results, presence of POUR, time until resolution of POUR, presence of postoperative urinary tract infection, results of postoperative Voiding Symptom Survey.

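### High-grade cystocele leads the plan's own list of risk factors for retention, but the data list has no planned field for cystocele grade, so a possible precision gain and a planned balance check are forgone

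*Combined protocol and SAP*

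**What the plan says.** The Background lists four risk factors for retention in this population: "most notably high grade cystocele, higher intra-operative blood loss, urinary retention prior to surgery, and early removal of foley catheter in elderly patients".

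The data list under Procedures opens with "Data collected will include: Study number, MRN, age, race, BMI" and goes on to parity, ASA class, tobacco use and several urodynamic measurements. On prolapse it has "preoperative diagnosis particularly of stress urinary incontinence or pelvic organ prolapse", and later "surgery performed, surgical complications, estimated blood loss, voiding trial results, presence of POUR". It has no item for cystocele stage, prolapse grade or compartment.

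Statistical considerations says that comparisons between the arms will be "evaluated with univariate and multivariate logistic regression as appropriate". It names no covariates and does not say which model is primary. Procedures says only that patients will be randomised to tamsulosin or placebo, and mentions no stratification.

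**The concern.** Of the four named risk factors, few can serve as a baseline covariate in this trial:

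- **Prior retention.** "History of urinary retention" is an exclusion criterion, so little or no variation is expected.
- **Blood loss.** It is measured after study drug has started, so it is not a baseline variable and should not be adjusted for in the treatment comparison.
- **Early catheter removal in elderly patients.** Every participant is due to have the catheter overnight and removed on postoperative day 1, so what varies is age, and age is already listed.
- **High-grade cystocele.** It is fixed before randomisation, varies between patients, is named first, and has no planned field.

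Two things are at stake. A prognostic covariate in a logistic model usually buys some power at no cost in patients, and this trial is sized with no slack. Also, with no stratification stated, the arms may differ by chance on this factor. Without a planned field, the baseline table would not show the difference and the model would not allow for it.

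**Working it through.** **1. The plan's sample size.** Inputs from Statistical considerations: failure rates 30% and 10%, power 80%, alpha 0.05 (taken as two-sided). With unpooled variance:

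n per arm = (1.960 + 0.842)² × (0.30×0.70 + 0.10×0.90) / 0.20² = 58.87, so 59 per arm and 118 in total.

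This reproduces the plan's figure. The calculation takes no credit for covariates. Expected failures are 59×0.30 + 59×0.10 = 17.7 + 5.9 = 23.6, about 24.

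**2. What adjustment would add.** The documents give no prevalence of high-grade cystocele and no OR for its effect on a failed voiding trial, so both are assumptions and are varied. Trials were simulated with 59 per arm and 30,000 trials per setting. Overall failure rates were held at 30% and 10%, and logistic regression was fitted with and without one binary cystocele term. Unadjusted power is about 80-81% by likelihood-ratio test and 78-79% by Wald test. The change in power, in percentage points, over prevalence 20-40% is:

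| Cystocele OR | Likelihood-ratio test | Wald test |
|---|---|---|
| 1 | -0.5 to -0.4 | -0.2 to -0.1 |
| 2 | +0.2 to +0.5 | +0.4 to +0.6 |
| 3 | +0.9 to +1.3 | +1.3 to +1.7 |
| 4 | +2.0 to +2.6 | +2.6 to +3.0 |
| 6 | +3.7 to +4.0 | +4.0 to +4.5 |

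A separate run of 40,000 trials per setting gave about 3 points at OR 5. It also gave a gain of the same size over a model that already held arm, site and surgery type, with surgery type simulated as unrelated to cystocele.

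**3. Chance imbalance.** Assume 40% prevalence. A gap of 10 points or more means at least 6 patients, since 0.10×59 = 5.9. The SD of the difference in counts is √(2×59×0.40×0.60) = 5.32. With a continuity correction, P = 2×[1 - Φ(5.5/5.32)] ≈ 0.30. The exact binomial value is 0.301.

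**4. What such an imbalance does.** Failure risks without and with high-grade cystocele, at 40% prevalence and overall rates of 30% and 10%:

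- OR 3: control 20.7% and 43.9% (gap 23.2); tamsulosin 6.0% and 16.0% (gap 10.0).
- OR 5: control 16.7% and 50.0% (gap 33.3); tamsulosin 4.3% and 18.5% (gap 14.2).

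If a 10-point imbalance is split evenly between the arms, the difference shifts by 0.10 × the mean gap:

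- OR 3: 0.10 × (23.2 + 10.0)/2 = 1.7 points.
- OR 5: 0.10 × (33.3 + 14.2)/2 = 2.4 points.

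The target difference is 20 points.

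**The case against.** The strongest reply is that the plan promises nothing it fails to deliver. The 59 per arm is an unadjusted calculation, and randomisation protects the unadjusted comparison with or without cystocele grade. Both statements are correct. A reader might infer that the omission takes the trial below 80% power or biases the result, and the documents support neither reading.

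A reader might also attach one figure to the loss, such as 2 to 3.5 points of power. That needs an OR of roughly 4 to 6, and no section gives one. At OR 2 the gain is negligible, and at OR 1 adjustment costs slightly.

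It would likewise go too far to say that the model cannot use cystocele grade. The data list is not stated to be exhaustive, no covariate is barred, and Data security keeps the record number until analysis is complete or for more than two years, so the chart can still be consulted. Diagnosis, surgery performed and the urodynamic measurements may carry part of the same information. If surgery type tracks cystocele closely, the added gain would be smaller than simulated, because that correlation was not modelled.

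Finally, taking the imbalance shift from control-arm risks alone gives 2.3 to 3.3 points. That overstates it, because the gap in the tamsulosin arm is smaller.

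What survives is that the proxies do not record grade. A covariate retrieved and chosen after unblinding would also be open to a charge of data-driven selection. The more basic gap, that neither covariates nor primary model are named, strengthens the case for settling this in advance.

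**Conclusion.** The point holds as a missed, inexpensive improvement and not as an error in the sample size or a threat to validity. The plan names high-grade cystocele first and has no planned field for its grade, while its analysis section foresees "univariate and multivariate logistic regression as appropriate".

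The power forgone depends wholly on an assumed prognostic strength. It is nil or slightly negative if grade is not prognostic, about 1-1.5 points at OR 3, and about 3-4 points at OR 5 to 6, for prevalence 20-40%. The imbalance result (about a 30% chance of a gap of at least 10 points, with a 1.7 to 2.4 point shift for a 10-point gap) rests on an assumed 40% prevalence and OR 3 to 5. The shift is modest beside a 20-point target, but a planned field would make it visible and correctable.

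**What to change.** Add preoperative cystocele stage to the data list as a two-level field (none/low versus high grade), taken from the routine preoperative examination in the chart. Code patients without a cystocele as none/low so that they stay in the model, and state in advance how a missing grade will be handled.

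Before unblinding, name the primary logistic model and include this term with treatment arm. Keep other terms few, because only about 24 failures are expected. Show the factor by arm in the baseline table, and report the unadjusted failure rates beside the adjusted result.

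The cost is one REDCap field, minor chart abstraction, an occasional missing grade, and at most about 0.5 points of power if grade is not prognostic. Sample size and trial procedures do not change.
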